This human laboratory study will systematically determine the independent and interactive effects of expectancy and nicotine dose on reinforcing (behavioral economic demand), subjective, and topography outcomes. Participants (N=20) will complete 4 experimental sessions in which expectancy (labeling of “average” nicotine versus “very low” nicotine) and nicotine dose (15.8 mg/g versus 0.4 mg/g) are manipulated as within-subject variables. Participants will sample a study cigarette of these combinations at the start of each session and complete craving, mood, withdrawal, and subjective drug effect measures before and after smoking. Smoking topography will also be collected during cigarette administration to determine if expectancy and dose impact how one smokes – one way that cognitive or pharmacological effects can impact smoking behavior. Demand will be evaluated with an incentivized demand task using experienced outcomes to improve experimental rigor. Behavioral economic demand analyses will differentiate between effects attributable to consumption of a good at no or little cost (“demand intensity”) and consumption following increases in cost (“demand elasticity”).

4. Study Procedures

a. Study design, including the sequence and timing of study procedures (distinguish research procedures from those that are part of routine care).

General Overview

Participants reporting current tobacco cigarette use will complete this double-blind, within-subject laboratory study. Participation will require in-person screening and 5 laboratory sessions that will take over approximately 2 weeks. We plan to recruit up to 25 participants to fully complete the study and will enroll up to 32 participants to account for possible attrition. Potential volunteers will participate in a brief telephone screening after responding to posted advertisements (e.g., community postings, radio). Those meeting initial inclusion/exclusion criteria in telephone

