screening will be scheduled for in-person screening at our research unit. Laboratory screening will include health history, drug history, and physical examination. Those passing full screening will participate in 1 practice session with procedures identical to experimental sessions but using the participant's own-brand cigarette. This practice session will serve to acclimate the participant to the study procedures, account for practice effects, and provide data for exploratory comparisons with own-brand cigarette data. Following practice sessions, each participant will complete 4 experimental sessions in which nicotine content (15.8 mg/g versus 0.4 mg/g) and expectancy (participant instructed "average" versus "very low" nicotine; see details below) are manipulated as within-subject variables. The full combination of sessions will be 15.8 told average; 15.8 told low; 0.4 told average; 0.4 told low completed in a randomized order.

Practice and Experimental Session Timeline

Participants will complete 4 experimental sessions lasting about 4 hours. Upon arrival to the laboratory, carbon monoxide will be collected to verify 8-hour abstinence as indicated by a CO <50% of the value obtained a screening (e.g., Mercincavage et al., 2016). A battery of subjective effect measures will be collected prior to cigarette administration including the Minnesota Nicotine Withdrawal Scale (MNWS; Toll et al., 2007), the Questionnaire on Smoking Urges (QSU; Cox et al., 2001), and the Positive and Negative Affect Scale (PANAS; Watson et al., 1988) measuring nicotine withdrawal, cigarette craving, and mood, respectively.

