Primary Analysis: Low nicotine expectancy and low nicotine dose will result in lower demand with lowest demand in combination: Demand variables will be computed and transformed if non-normal (e.g., log-transform). Analyses will use a 2x2 repeated measures ANOVA with the within-subject factors of expectancy (“average” and “very low”) and dose (15.8 mg/g and 0.4 mg/g). Hypothesis 1 will be supported by significant main effects indicating significantly lower demand under “very low” expectancy and 0.4 mg/g conditions. A significant interaction would also indicate different-than-additive effects of expectancy and dose. Such an interaction is plotted in Figure 3 with hypothetical data of a greater reduction in demand intensity by nicotine content under the “very low” expectancy condition.

Secondary Analysis: Low nicotine expectancy and low nicotine dose will result in lower positive subjective effects (H2) and lower puff volume (H3) with lowest values in combination. A 2x2 ANOVA will also be used for puff topography and subjective effect measures with similar predictions as Hypothesis 1. Measures with pre- and post-cigarette administration measures will use a 2x2x2 ANOVA including a within-subject factor of time. We expect less reduction in withdrawal and craving with low nicotine expectancy and low nicotine dose indicated by significant interactions with time.

Sample Size Justification: With respect to power, simulation of a 2x2 repeated measure ANOVA based on estimates from preliminary demand data (e.g., nicotine dose effect, SD) identified 82% power to detect a main effect under additive effects. More generally, the sample provides 80% power to detect a medium-large bivariate within-subject effects ($d_z = 0.66$). This project is considered a pilot project and therefore we have focused on a feasible sample size to generate signals of the behavioral relevance for expectancy in reduced-nicotine policy to inform scientific rationale for future projects. These findings will also provide evidence for the feasibility of within-session procedures with incentivized consequences for rapidly evaluating demand of experimental commodities, thereby serving as preliminary “proof-of-concept” data for a variety of proposals evaluating the reinforcing effects of novel experimental commodities. We will enroll up to 25 participants that complete the study to ensure that at least 20 provide fully systematic data on primary demand outcomes.

d. Early stopping rules.

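### Session order is described only as randomised and the ANOVA has no session term; a Williams-square list plus an added session factor is a cheap gain in precision

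*Combined protocol and SAP*

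**What the plan says.** Section 4.a (General Overview) lists the four dose-by-label conditions as "15.8 told average; 15.8 told low; 0.4 told average; 0.4 told low completed in a randomized order". The protocol names no counterbalancing, Latin or Williams square, or blocking, and does not say how the orders are produced. Its one stated measure against order effects is the own-brand practice session, meant among other things to "account for practice effects".

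Section 6.c states: "Analyses will use a 2x2 repeated measures ANOVA with the within-subject factors of expectancy", with dose as the other factor. The secondary models use the same two factors, plus time for measures taken before and after smoking. None of them has a term for session position, sequence or preceding condition.

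On numbers, the end of section 3 says "Participants (N=20) will complete 4 experimental sessions". Section 4.a allows up to 25 completers and "will enroll up to 32 participants to account for possible attrition", and section 6.c wants enough completers to "ensure that at least 20 provide fully systematic data on primary demand outcomes".

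**The concern.** Each participant hears both labels and smokes both doses over about two weeks, and is asked to estimate nicotine content after every session. Demand could drift over the four sessions, and a session in which label and dose disagree could colour belief in the next label. One practice session cannot rule out a later trend, and it cannot balance which condition follows which. The documents give no size for either effect, so both are plausible risks only.

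If orders are drawn independently from the 24 possible ones, about 20 participants are too few for position and preceding condition to even out. With no session term, a trend adds to the error of every within-subject contrast: dose, expectancy and their interaction. The power statement leaves little slack for that.

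**Working it through.** **Inputs.** From section 6.c: 80% power at d_z = 0.66. From section 3: N = 20. Assumed: two-sided alpha of 0.05 (not stated), within-subject SD of 1 per condition, and the sizes of any trend or carry-over.

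**1. The plan's own figure.** A paired t-test with N = 20, d_z = 0.66 and 19 df has noncentrality 0.66 × √20 = 2.95 and power 79.95%. This reproduces "the sample provides 80% power to detect a medium-large bivariate within-subject effects". The separate claim, "identified 82% power to detect a main effect under additive effects", cannot be checked because its effect and SD are not given.

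**2. Imbalance under independent random orders.** For one participant, the difference between the doses in mean session number is −2, −1, 0, 0, +1 or +2 with equal chance, so its variance is (4 + 1 + 0 + 0 + 1 + 4)/6 = 1.667. Over 20 participants the SD is √(1.667/20) = 0.29 sessions. The same holds for the two labels. In 20,000 simulated allocations:

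- the 95th percentile of the absolute difference was 0.55 sessions;
- first-session counts of the four conditions differed by 4 or more in 69%;
- the 12 ordered pairs of consecutive conditions had median smallest and largest counts of 2 and 8 (target 5), and some pair occurred at most once in 25%.

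A Williams square with 5 participants per sequence has every position count and every pair count equal to 5.

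**3. Cost of a trend under the planned ANOVA.** A linear trend of b SD per session raises the variance of a participant's dose contrast from 1 to 1 + 1.667b². At b = 0.4 this is 1.267, so the effective d_z is 0.66/√1.267 = 0.586 and power is about 70% (simulated 69.8%). At b = 0.2 simulated power is 77.4%. Type I error stays at about 5.0%.

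**4. A Williams list alone.** With b = 0.4 and no session term, simulated power is 67.5% and type I error is 2.2%. The trend no longer moves the estimate, but it still inflates the error term.

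**5. Session term added (pooled within-subject error, 54 df).**

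| Orders | Variance of dose effect | Power at d_z = 0.66 |
|---|---|---|
| Williams, 5 per sequence | 1/20 = 0.0500 | 82.6% |
| Independent random, average | about 6% higher | 80.5% |
| Independent random, worst 5% | about 16% higher | about 77% |

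These hold whatever the trend, because session is in the model. At b = 0.4, the session term with pooled error takes power from about 70% to 80.5%, and balance adds the last 2 points. With no trend, the 82.6% against the planned 79.95% reflects the larger error df (54 against 19), because imbalance then costs the unadjusted ANOVA nothing. Pooling assumes equal error variance across the three contrasts.

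With first-order carry-over terms as well, power is 78.8% for Williams and 74.3% on average for random orders (5th percentile 66.3%).

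**6. Attrition.** If 32 are balanced and a random 20 analysed, first-session counts still differ by 4 or more in 28% (random orders: 69%), and variance is about 2% above the ideal. The saving from balance is then about 6% − 2% = 4%.

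**7. Carry-over bias.** In three of every four sessions there is a preceding session. In a balanced list that session has the same dose one time in three and the other dose two times in three. An assumed dose carry-over of 0.3 SD therefore shifts the unadjusted dose effect by 0.3 × 3/4 × (1/3 − 2/3) = −0.075 SD. Independent random orders give the same expected shift.

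**The case against.** Random order is a legitimate design. Without carry-over it gives an unbiased estimate and correct type I error, and the study calls itself a pilot sized for feasibility. That stands: a reader might infer that the primary comparison is biased or invalid, and neither the documents nor the calculation supports this.

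The protocol is also silent rather than explicit. Random allocation to balanced sequences would fit its wording, so one cannot conclude that orders are drawn independently or that balance was rejected. The figures for random orders are conditional on independent draws. If a balanced list exists, the protocol need only describe it, but the missing session term would remain.

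It is also tempting to say that a Williams square would remove the imbalance at no cost. It would not. Exact balance needs equal numbers of analysed participants per sequence. Attrition works against that, 25 is not a multiple of four, and unsystematic demand data come to light only after sessions are run. Balance does not remove carry-over bias, and the list alone gains no power under the planned ANOVA.

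Finally, four fixed sequences are more predictable than 24. Section 4.a keeps dose from all research staff, but the person delivering the label knows the label. Under two of the three distinct ways of assigning conditions to the square, the four label sequences all differ and can be told apart after two sessions. A label-deliverer who knew the square could then work out the dose. This is a real cost, but a suitable assignment avoids it.

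**Conclusion.** This is a cheap improvement, not an error in the plan. The order description should be made specific and the models should carry session position. For N = 20, d_z = 0.66 and two-sided 5%, the two changes together take power from about 80% to between 82% and 83% if there is no trend, and from about 70% to 83% under an assumed trend of 0.4 SD per session. Under a trend the session term does most of the work. Balance contributes about 2 points, or 6% of variance, with complete data, and about 4% of variance after attrition from 32 to 20. It also makes carry-over easier to estimate. The size of any trend or carry-over is an assumption, as are independent draws of order and a pooled error variance.

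**What to change.** Make both changes together, before allocation starts.

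1. In section 4.a, state that participants are randomised in blocks of four to the four sequences of a Williams square, and that a replacement takes the sequence of the participant replaced where possible. This gives 5 per sequence at 20 and 6 or 7 at 25. Choose an assignment in which the label order does not reveal dose. One such set (A = average label, V = very-low label) is:
   - 15.8 A, 15.8 V, 0.4 V, 0.4 A
   - 15.8 V, 0.4 A, 15.8 A, 0.4 V
   - 0.4 A, 0.4 V, 15.8 V, 15.8 A
   - 0.4 V, 15.8 A, 0.4 A, 15.8 V

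   It has only two label orders (AVVA and VAAV), each shared by two sequences with opposite doses in every session.
2. In section 6.c, add session position (1 to 4) as a factor to the primary and secondary models, fitted as a within-subject linear or mixed model. Report any first-order carry-over analysis as a sensitivity analysis.
3. Conceal the list and the block size from all session staff, including the person who delivers the label.

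The cost is a new list, a few sentences and 3 degrees of freedom. No extra participants or visits are needed.

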
2. Objectives (include all primary and secondary objectives)

Primary objective: Determine the interaction of expectancy effects and nicotine dose on behavioral economic demand for reduced-nicotine cigarettes. Demand will be evaluated using an incentivized demand task with experienced outcomes to provide experimental rigor. We hypothesize lower demand (via intensity and elasticity) for “very low” labels and low nicotine content cigarettes, with the lowest demand when in combination.

Secondary objective: Determine the interaction of expectancy effects and nicotine dose on subjective effects and smoking topography for reduced-nicotine cigarettes. Participants will sample the study cigarette at the start of each session and complete craving, mood, withdrawal, and subjective drug effect measures before and after smoking. Smoking topography will also be collected during cigarette administration to determine if expectancy and dose impact how one smokes (another primary way cognitive or pharmacological effects can impact smoking). Based on prior research, we hypothesize lower positive subjective effects and lower puff volume for “very low” labels and reduced-nicotine cigarettes with the lowest values for their combination.

3. Background (briefly describe pre-clinical and clinical data, current experience with procedures, drug or device, and any other relevant information to justify the research)

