Participants will complete demand procedures following the standardized cigarette administration (see details below).. A three hour smoking period will follow demand task completion in which cigarette units purchased at a randomly selected price from the demand task are available to smoke. Topography will be collected during this time, but will not be directly compared across sessions due to differences in the number of cigarette units obtained across participants and sessions depending on demand task selections. Sessions will conclude after the 3-hour period. Following completion of all experimental sessions (or earlier if participation is discontinued), participants will be debriefed about the study and experimental manipulations. Prior to debriefing, the validity of the expectancy blind and delivery will be assessed by asking participants what they believed the study purpose was. Participants will also be asked about the estimated nicotine content of cigarettes at the end of each session to evaluate validity of the manipulation.

Description of Behavioral Economic Demand

An ***incentivized purchase task*** will be used to evaluate demand involving within-session incentivized consequences. The purchase task procedure is a well-validated experimental procedure with meta-analyses supporting concurrent validity (González-Roz et al., 2019) and sensitivity to experimental manipulations (Acuff et al., 2020). The current study will use a procedure with experienced consequences to improve rigor. Participants will receive a study income (\$50 of the \$100 session payment) to allocate for purchasing. Instructions will stipulate that one price will be randomly selected to be *real*—meaning that the cigarette units purchased at the selected price will be available to consume during a 3-hour period and money deducted from the total session payment. Instructions will stipulate that these will be the only cigarettes available during that time and that cigarettes cannot be stockpiled (i.e., will only be available for consumption in the laboratory).

Study Cigarettes

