Participants will be instructed that this cigarette is either “the same level of nicotine as your usual brand” or “a very low level of nicotine compared to your usual brand” but blinded to actual nicotine content. This manipulation will be necessary for the expectancy variable and success of the study protocol. A thorough debriefing about the study will occur at study completion or if a participant discontinues participation early. Dose will be double-blind such that neither research staff nor participants know the dose. Expectancy will be double-blind such that research staff who collect outcome assessments will not know the exposure participants receive (i.e., a separate member of research staff will deliver the manipulation).

d. Justification of why participants will not receive routine care or will have current therapy stopped.

N/A. This study does not involve therapy.

e. Justification for inclusion of a placebo or non-treatment group.

N/A. This study does not involve placebo.

f. Definition of treatment failure or participant removal criteria.

Participants will be removed from this study if they fail to comply with protocol instructions that are outlined in the consent form or if they are not medically or psychologically suitable to continue.

g. Description of what happens to participants receiving therapy when study ends or if a participant's participation in the study ends prematurely.

The study procedures are not designed to provide therapy for cigarette smoking related problems. Participants will be individuals who do not have immediate plans to quit smoking.

Inclusion/Exclusion Criteria

Inclusion criteria:

- 21 years or older (i.e., individuals under 21 may not legally purchase tobacco products).
- Smoke five or more cigarettes per day for the past six months (e.g., Mercincavage et al., 2016).
- Biological confirmation of cigarette use: have an expired carbon monoxide (CO) level of more than 8 ppm and a urinary cotinine level of more than 100 ng per milliliter at screening.

General medical exclusion criteria:

- Intention to quit smoking in the next 30 days (unethical to recruit treatment seeking participants).
- Daily use of nicotine-containing products other than machine-manufactured combustible cigarettes.
- Serious medical or psychiatric disorder precluding participation by study physician guidance.

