Demand tasks will be analyzed for derived and curve-observed measures. Derived measures include demand intensity (Q0; consumption at unconstrained price) and demand elasticity (a measure of sensitivity of consumption to changes in price) and will be computed using the exponential demand equation $\text{LogQ} = \text{Log Q0} + k(e^{-\alpha Q0C}) - 1$ (Hersh & Silberberg, 2008). The independent variable C is cost (price/cigarette), the dependent variable Q is consumption (cigarettes purchased at a particular price), the scaling parameter k indicates the range of LogQ in the observed data. Free parameters are Q0 (demand intensity) and α (demand elasticity). Should zero-dense data be observed, a modified exponentiated form of the demand equation will be considered (Koffarnus et al., 2015; Strickland et al., 2016). Observed measures include Pmax (price at maximum consumption), Omax (maximum consumption), and breakpoint (Breakpoint-1; the price of last non-zero demand).

b. Secondary outcome variables. Descriptions of Outcome Measures

Subjective Effect Measures

Subjective effect measures will include a measure of nicotine withdrawal (MNWS), smoking craving (QSU), mood (PANAS), and cigarette subjective experience (Drug Effect Questionnaire). These measures will be collected upon arrival to the laboratory (i.e., immediately prior to cigarette administration) and following the 10-minute standardized smoking period. All measures will be scored using standard procedures.

Smoking Topography

Six measures of smoking topography will be collected including: total puff volume, mean puff volume, mean puff duration, mean inter-puff interval, mean maximum flow rate, and number of puffs (Higgins et al., 2018). These measures will be collected during the 10-minute standardized cigarette smoking period using a custom smoking topography system currently in use in our laboratory.

c. Statistical plan including sample size justification and interim data analysis.

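### Should the exponentiated demand model be made primary because zero purchases cannot enter the log-scale fit?

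*Combined protocol and SAP*

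**What the plan says.** Section 6a names Q0 and alpha as the primary metrics and estimates both from an exponential curve fitted to LogQ, in which "the scaling parameter k indicates the range of LogQ in the observed data". On zeros it has one conditional sentence: "Should zero-dense data be observed, a modified exponentiated form of the demand equation will be considered". Two methodological papers are cited for that alternative. The section sets no threshold for zero-dense data. It does not say what happens to zeros in the default fit, or whether k is pooled over sessions. Zeros are foreseen, because the observed measures include "breakpoint (Breakpoint-1; the price of last non-zero demand".

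Section 2 predicts movement in both metrics: "We hypothesize lower demand (via intensity and elasticity". The Background sets the aim of telling them apart: "Behavioral economic demand analyses will differentiate between effects attributable to consumption of a good at no or little cost", as opposed to consumption once the price rises. Section 4a says that "cigarette units purchased at the selected price will be available to consume during a 3-hour period" but gives no unit size, while Section 6a counts whole or part cigarettes without saying which. The documents give no price list.

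Section 6c analyses the derived metrics by a 2x2 repeated measures ANOVA. It states 80% power at d_z = 0.66, aims for at least 20 participants with usable demand data out of up to 25 completers, and describes the project as a pilot.

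**The concern.** The logarithm of zero does not exist, so a no-purchase price cannot enter the default fit. If zeros are dropped and k is taken from the positive purchases, the smallest purchase unit becomes the floor of the curve. A session with lower Q0 starts closer to that floor and has less visible room to fall, so its fitted alpha can come out too low. Hypothesis 1 expects Q0 to fall and alpha to rise together, so this error would work against the trial's own prediction and blur the separation that the Background promises.

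Two further features make it look serious. The alternative model is only to be considered, on an undefined trigger, so the model for both primary metrics could be picked after the data are seen. And low Q0 is plausible: purchases cover three hours, cannot be stockpiled, and the entry criterion is "Smoke five or more cigarettes per day for the past six months". A Q0 of 15 means one cigarette every 180/15 = 12 minutes; a Q0 of 7 means one every 180/7 = 26 minutes.

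**Working it through.** **1. The plan's own figure.** For a paired t test (two-sided 0.05, assumed) with n = 20 and d_z = 0.66, the noncentrality is 0.66 x sqrt(20) = 2.95 on 19 degrees of freedom, and power is 0.7995. The stated 80% is reproduced. Effects 10%, 20% and 25% smaller give 71%, 61% and 56%. With n = 25, d_z = 0.66 gives 89% and an effect 25% smaller gives 66%. Attenuation would therefore matter if it occurred.

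**2. The mechanism.** The curve is read as log10 Q = log10 Q0 + k(e^(-alpha Q0 C) - 1), which returns Q0 at zero price. (As printed, the -1 falls outside the bracket and would give Q0 x 10^(k-1); this is a slip in typesetting.) With whole cigarettes the smallest positive purchase is 1. A fall of 0.15 in log10 Q0 takes a Q0 of 7 to 7 x 10^(-0.15) = 4.96. The visible drop to the floor shrinks from log10 7 = 0.85 to log10 4.96 = 0.70.

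**3. Purchases rounded to the nearest unit.** Assumptions: N = 20, 400 trials per scenario, 16 prices up to $20 or $50, a $50 cap, and reference alpha 0.003 or 0.006. True dose effects are -0.15 on log10 Q0 and +0.15 on log10 alpha. Each row compares zeros omitted with the exponentiated form.

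| Unit, reference Q0 | Alpha effect, omission vs exponentiated | Power loss |
|---|---|---|
| Whole, 7 | 17-30% lower | 11-27 points |
| Whole, 7, k fixed at 2 | 14-22% lower | 5-18 points |
| Whole, 15 | 10-15% lower | 6-12 points |
| Half units | 4-13% lower | 1-12 points |
| Quarter units | 0-9% lower | -3 to 10 points |

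Over all whole-cigarette scenarios the mean power loss is 14 points, or 8 with k fixed, so nearly half comes from the k rule and not from the zeros. A separate run with other price lists gave 5-22% lower at Q0 7.

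**4. Purchases rounded down.** Here a cigarette is bought only if a full one is wanted. The setting is whole cigarettes, Q0 7 or 15, the same alphas, k from the observed range, and 120 simulated participants per scenario. Medians are shown; they carry simulation error in the second decimal.

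| True alpha effect | Zeros omitted | Exponentiated |
|---|---|---|
| 0.15 (Q0 also falls) | 0.145 to 0.162 | 0.159 to 0.193 |
| 0 (only Q0 falls) | +0.003 to +0.019 | +0.015 to +0.056 |

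The exponentiated form overstates by up to 0.193/0.15 - 1 = 29%, and when only Q0 falls it shows a false rise in alpha, the direction that Hypothesis 1 predicts. A rerun at Q0 5-7 agreed: 0.14-0.16 for omission, 0.18-0.21 exponentiated, and a false rise of about 0.02 to 0.06. Omission is not clean either: in two Q0 7 scenarios a few near-flat sessions pulled its mean, though not its median, down to 0.084 and 0.126.

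**5. A separate simulation.** Q0 is cut by 40%, alpha is truly unchanged (ratio 1) at 0.02, and k = 2 is correct. Each person's alpha is identical in both sessions, so small shifts reject easily. Entries are the median alpha ratio and the share of n = 20 studies rejecting equal alpha.

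| Q0, purchases | Zeros omitted | Exponentiated |
|---|---|---|
| 3, nearest whole unit | 0.76, 83% | 1.02, 3% |
| 3, continuous, zero below 0.5 | 0.98, 8% | 1.11, 96% |
| 5, nearest whole unit | 0.92, 51% | 1.01, 4% |
| 5, continuous, zero below 0.5 | 1.00, 5% | 1.07, 39% |
| 8, nearest whole unit | 0.97, 27% | 1.01, 4% |
| 8, continuous, zero below 0.5 | 1.00, 4% | 1.03, 10% |

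The ranking of the two models reverses with the purchasing rule. For buyers who hold consumption constant and then stop, neither fit is clean: false alpha findings were 6-29% under omission and 5-37% under the exponentiated form.

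**6. Cost of leaving the choice open.** With no effect on either metric (6,400 whole-unit trials, nearest rounding), omission rejects in 4.8%, the exponentiated form in 5.0%, and 5.7% if either could be reported. The Q0 effect (true -0.15) is -0.152 to -0.163 under omission and -0.149 to -0.152 under the exponentiated form.

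**The case for a change.** The best case for a change is this. Whole-cigarette purchasing is a natural reading of Section 6a, low Q0 is likely in a three-hour session, and separate simulations under nearest-unit rounding all found attenuation. At a reference Q0 of 4 it becomes severe: an alpha effect of 0.047-0.091 against 0.133-0.148, and power of 10-33% against 58-75%. If only Q0 falls from a reference of 7, omission rejects equal alpha in 9-14% of trials, against 3-6%. The plan has little spare power, the alternative model is already named, and adopting it costs a few lines of text and code.

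Part of this stands. The trigger is undefined, the wording does not commit, and the treatment of zeros, k and unfittable sessions is unstated. If people buy whole cigarettes by rounding to the nearest unit and buy few of them, dropping zeros weakens the alpha contrast.

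What does not stand is the step from there to a preferred model. It depends on a rounding rule that the documents do not give. Under rounding down, or with small amounts cut to zero, the exponentiated form is the more biased of the two and errs towards the hypothesis, whereas the error from omission under nearest rounding is conservative. That zeros would be dropped at all is also an inference: Section 6a never says so, and it names an alternative for data with many zeros.

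**Conclusion.** No change to the plan follows. Which fit serves alpha better depends on purchase increment, rounding and Q0, none of which the documents state. Under assumed inputs, omitting zeros understates the alpha effect by 17-30% relative to the exponentiated form (whole cigarettes, nearest rounding, Q0 7), while the exponentiated form overstates it by up to 29% (whole cigarettes, rounding down). Requiring the exponentiated form would exchange a conservative error under one purchasing rule for an anti-conservative one under another.

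What is left is missing detail that analysts can settle sensibly when they see the share of zeros. Both models are named, and breakpoint, which is read directly from where purchasing stops, is planned alongside them. The consequence of that freedom is small where it could be measured: 5.7% against a nominal 5% when nothing changes, Q0 little affected, and every rejection under a true alpha effect at Q0 7 or 15 in the right direction (nearest rounding). For a study that Section 6c presents as a pilot to produce signals for later work, this is a fair trade-off. The conclusion rests on assumed price lists, variances and parameters throughout; very low Q0 with whole-cigarette buying is where it is weakest.
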